### **5.2.2.2 Win Ratio Estimates**

In order to evaluate the magnitude of treatment effect in the primary effectiveness endpoint, the unmatched win ratio estimates (Pocock 2012) will be provided as well as the corresponding 95% confidence interval (CI).

The unmatched win ratios are formed by comparing every subject in the treatment group with every subject in the control group. Specifically, if we let  $n, m$  be the number of subjects in the treatment and control groups, respectively, then we make  $n \times m$  paired comparisons. The win ratio is then calculated as  $N_W/N_L$  where  $N_W$  and  $N_L$  are the total number of pairwise wins and losses, respectively, for the treatment group.

Following Bebu (2016), logarithm of  $\widehat{WR} = N_W/N_L$  has an asymptotic normal distribution with mean and variance specified in (2.6) of the paper. Therefore, the estimated WR and the 95% Confidence Interval (CI) will also be derived and presented from the sample distribution of  $\log(\widehat{WR})$  using Delta method with the exponential transformation.

### **5.2.2.3 Missing Data Handling**

There is no missing data imputation for the effectiveness analysis of the primary endpoint. Any missing values in the Win/Loss evaluation of pairs for each component will be considered as tie, and the Win/Loss will be determined based on the 3 steps described above.

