11.1. Statistical Power and Sample Size Determination

Up to 140 subjects meeting the study inclusion criteria (**Section 4.4.1**) will be randomized in a 1:1 ratio to the treatment and control arms. As noted above (**Section 6.2**), in order to maintain the balance between sites in terms of numbers of subjects randomized, study sites will be capped at randomizing a maximum of 15% of the overall study sample. Allowing for 5% dropouts, at total of 114 subjects (57 per arm) are expected to be evaluable for effectiveness and safety. Sample size is based on assumed effect size for the primary effectiveness Win Ratio sub-components (**Table 3**), and can be calculated via an iterative simulation process with programming code available in an appendix to Redfors et al. (2019).[11] With a Finkelstein – Schoenfeld test, a total of 57 subjects per arm ensures power of $\geq 99.7\%$ for the primary effectiveness endpoint at the final analysis, using a two-sided alpha (α) of 0.05. [10] With this same per arm sample size, power for the key secondary endpoint is estimated at $>99.9\%$ assuming a $40\% \pm 40\%$ mean difference between treatment and control, based on a two-

sample t-test assuming equal variance and a two-sided alpha of 0.05. For the 24-hour CTD secondary endpoint, assuming a treatment arm volume of 480 ± 253 mL and control arm volume of 800 ± 253 mL [8] [a discount is applied (see **Table 3** for details) to bring the Active arm up to ~40% reduction on the Control arm], power is similarly estimated at >99.9%. Power for comparisons of platelet transfusions between the treatment arm (0.32 ± 0.9 units) and control arm (1.6 ± 2.2 units) [13] is estimated at 98.0%, based on a two-sample t-test assuming unequal variance and a two-sided alpha of 0.05. Similarly, power for PRBC transfusions between the treatment arm (1.3 ± 2.1 units) and control arm (4.4 ± 5.7) [13] is estimated at 96.7%.

Overall study sample size is designed to provide adequate power for the primary effectiveness endpoint, the key secondary endpoint, and succeeding three secondary endpoints. Sample size and power for all secondary endpoints were calculated using PASS 2021 (NCSS, LLC. Kaysville, UT, USA, ncss.com/software/pass).

The null hypothesis for the primary composite endpoint is represented by:

H_0 : The distributions of the components are the same in the two treatment groups.

The alternative hypothesis for the primary composite endpoint is represented by:

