H_A : For at least one component, the distribution is different between the treatment groups.

Table 3. Win Ratio Effect Size Assumptions with Power and Sample Size Estimates

n Per Group	Effect Size						Power	
	Component #1		Component #2		Component #3			
	Fatal Bleeding		UDPB (Class ≥ 2)		24hr CTD			
	Treatment Event	Control Event	Treatment Event	Control Event	Treatment Mean (SD)	Control Mean (SD)		
N=57	3.0%	3.0%	24.3%	40.5%	480 (253)	800 (253)	≥99.7%	

Notes: n = number; UDPB = Universal Definition of Perioperative Bleeding; CTD = chest tube drainage (volume [mL]).

Component #1 minimum rates of 3.0% assumed as a conservative approach.

Component #2 rates based on Russo et al. (2019), however, with a discount applied to bring the Treatment arm up to ~40% reduction on the Control arm. [14]

Component #3 rates based on Hassan et al. (2019), however, with a discount applied to bring the Treatment arm up to ~40% reduction on the Control arm. [8]

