11.5. Treatment of Missing Data

Every effort will be taken to obtain data entry compliance of all critical fields during the course of the study. The study assumes up to 5% of the data may be missing. Reasons for missing data will be collected and a distribution of the prognostic factors in subjects with and without missing data will be compared to identify any confounding factors. Sensitivity analyses will be conducted to assess the sensitivity of the results to assumptions underlying the missingness mechanism. Details will be provided in the SAP.

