## 5.2 Analysis of the Primary Effectiveness Endpoint

The primary effectiveness endpoint is a hierarchical composite endpoint with three components ranked in descending order of clinical importance as follows:

1. Fatal perioperative bleeding event (occurring within 48hrs post index procedure)
2. Moderate, severe, or massive perioperative bleeding events according to UDPB classification (UDPB  $\geq 2$ ) (Dyke 2014)
3. 24-hour chest tube drainage (CTD) (mL) following surgery.

The hypothesis for the primary effectiveness endpoint will be tested using Finkelstein-Schoenfeld test (Finkelstein et al 1999). In constructing the test, “wins”, “losses”, or “ties” for all pairs of subjects in sequential comparisons according to the hierarchical order of the components of the primary composite endpoint.

Specifically, let the primary effectiveness endpoint  $Y = (y_1, y_2, y_3)$ , we evaluate win/loss for all subject pairs  $(i, j)$  as follows:

**Step 1:** Pair  $(i, j)$  is evaluated at the first component: fatal perioperative bleed occurring within 48 hours of the index procedure, with a binary (yes/no) outcome. It requires one subject not to experience the event and the other subject to experience the event in order to declare a “winner”, i.e.,

the subject  $i$  wins if  $y_1[i]=\text{no}$ ,  $y_1[j]=\text{yes}$ ; loses if  $y_1[i]=\text{yes}$ ,  $y_1[j]=\text{no}$ .

Otherwise, this is a tie for the pair in the first component and move to Step 2

**Step 2:** The second component - moderate, severe, or massive perioperative bleeding events according to UDPB classification  $\geq 2$  is also a binary (yes/no) outcome and follows the same process as step 1 for determining a win ( $y_2[i]=\text{no}$ ,  $y_2[j]=\text{yes}$ ) or a loss ( $y_2[i]=\text{yes}$ ,  $y_2[j]=\text{no}$ ) for the subject  $i$ . Otherwise, this is a tie at the second level and move to Step 3.

**Step 3:** The third component is 24-hour chest tube drainage (mL) following surgery. This is a quantitative (continuous) outcome where a lower drainage is better and therefore the subject with less drainage is declared the winner, i.e.,

the subject  $i$  wins if  $(y_3[i] < y_3[j])$ ; loses if  $(y_3[i] > y_3[j])$

Otherwise, they tie on the primary effectiveness endpoint.

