### 5.2.2.1 Significance Test

The primary hypothesis will be tested at the two-sided significance level of 0.05 using Finkelstein-Schoenfeld test statistics (Finkelstein et al 1999). All pairs of subjects are compared, regardless of the treatment groups, and a score  $W_{ij} = 1, -1$  or 0 is assigned to the pair  $(i, j)$  depending on whether subject i was a winner, a loser, or the comparison was inconclusive.

The test statistic is  $T = \sum_i D_i W_i$ , where  $D_i$  is the indicator variable for the treatment and  $W_i = \sum_j W_{ij}$ . Under the null distribution of no treatment effect, T is asymptotically normally distributed with mean 0 and variance  $\frac{n*m}{N*(N-1)} * \sum_i W_i^2$ , where n and m are the sample size for the treatment and control group respectively, and  $N = n + m$ .

Therefore, a significance test based on the standardized T statistic denoted by Z-statistics will be used to test the null hypothesis. The p-value will be provided and compared at the significance level of 0.05.

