## **5.2.3 Sensitivity Analysis**

In order to assess the robustness of the primary effectiveness analysis a bootstrap method will be used to estimate the win ratio for the treatment. Instead of using the asymptotic variance for  $\log \widehat{WR}$ , a bootstrap resampling from the original primary effectiveness endpoint will be performed for 1000 times to obtain a bootstrap estimate of variance. With this bootstrap variance estimate, the 95% CI will be derived similarly as the primary effectiveness analysis.

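### Scoring every missing component as a tie means a non-bleeding death before 24 h with UDPB<2 can never lose a pair, and the SAP has no missingness sensitivity analysis for the primary endpoint

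*SAP*

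**What the plan says.** SAP 5.2 compares pairs in three steps. Step 1 is "fatal perioperative bleed occurring within 48 hours of the index procedure, with a binary (yes/no) outcome", so a death from another cause scores no event. Step 2 is UDPB>=2, yes or no. Step 3 is 24-hour CTD, where the lower volume wins. SAP 5.2.2.3 imputes nothing: "Any missing values in the Win/Loss evaluation of pairs for each component will be considered as tie".

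Protocol 9.2.6 accepts that 24 hours of drainage may not be recordable when a subject dies sooner. SAP 5.4.1.1 drops subjects whose CTD is missing because of death from the secondary CTD analysis. Neither document gives a rule for death in the primary composite.

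Protocol 11.5 expects up to 5% missing data and commits to more: "Sensitivity analyses will be conducted to assess the sensitivity of the results to assumptions underlying the missingness mechanism". It also promises a comparison of prognostic factors between subjects with and without missing data, and it leaves the details to the SAP. For the primary endpoint, SAP 5.2.3 contains one item: "a bootstrap resampling from the original primary effectiveness endpoint will be performed for 1000 times to obtain a bootstrap estimate of variance". SAP 5.2.4 repeats the primary analysis in the ITT, per-protocol and isolated-CABG sets.

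**The concern.** The tie rule turns an unobservable outcome into a neutral one. For a subject who died early of a non-bleeding cause and had UDPB<2, steps 1 and 2 can only be won or tied, and step 3 is always a tie. The worst clinical outcome therefore gets a score with wins and no losses.

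The planned robustness check cannot show what this does. The bootstrap resamples data already scored under the tie rule and changes only the variance estimate. The ITT, per-protocol and isolated-CABG runs use the same rule. In the ITT run, a randomized subject who never had the operation would have no components at all and would tie every pair. If early deaths were unequal between the arms, no planned analysis would show how far the win ratio depends on their scoring.

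**Working it through.** **Inputs.** Two-sided alpha is 0.05 (SAP 5.2.2.1: "The primary hypothesis will be tested at the two-sided significance level of 0.05"). Fatal bleeding is 3.0% in each arm (Protocol Table 3: "Component #1 minimum rates of 3.0% assumed as a conservative approach"). UDPB>=2 is 24.3% on device and 40.5% on control. CTD means are 480 and 800 mL, with SD 253 in Scenario 1 (Protocol 11.1: "assuming a treatment arm volume of 480 ± 253 mL and control arm volume of 800 ± 253 mL") and SD 500 in Scenario 2 (SAP Table 1). Components are taken as independent and CTD as normal, because the documents give no correlation or distribution.

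**Reproducing the plan.** Simulating the Finkelstein-Schoenfeld test with the SAP variance (4,000 trials) gives 91.6% for Scenario 2 at 65 per arm (stated 92.1%) and 99.5% for Scenario 1 at 57 per arm (stated 99.7%). Lognormal CTD gives 98.8% for Scenario 2 and does not reproduce the plan.

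**Which pairs matter.** SAP 5.2.2.1 says "All pairs of subjects are compared, regardless of the treatment groups". Within-arm pairs cancel when scores are summed over the device arm, so a device subject affects the test statistic and the win ratio through its net score (wins minus losses) against controls.

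**Early non-bleeding death on device, UDPB<2, CTD missing.** Win = 0.03 + 0.97 × 0.405 = 0.423. Loss = 0. Net = +0.423 in both scenarios, since CTD plays no part.

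**Device subject without a fatal bleed.** Let p be the probability of winning on CTD, p = Φ(320/(SD√2)): 0.814 in Scenario 1 and 0.675 in Scenario 2.
- UDPB decides a win: 0.757 × 0.405 = 0.307.
- UDPB decides a loss: 0.243 × 0.595 = 0.145.
- Pair passes to CTD: 0.757 × 0.595 + 0.243 × 0.405 = 0.549.
- Net = 0.03 + 0.97 × [0.307 − 0.145 + 0.549 × (2p − 1)].

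For a device survivor who also has UDPB<2, net = 0.03 + 0.97 × [0.405 + 0.595 × (2p − 1)].

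| Net score against controls | Scenario 1 | Scenario 2 |
|---|---|---|
| Early non-bleeding death, UDPB<2 | +0.423 | +0.423 |
| Average device subject without fatal bleed | +0.522 | +0.373 |
| Device survivor with UDPB<2 | +0.786 | +0.624 |

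The first two rows cross at a CTD SD of about 386 mL.

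**Same death on control.** Against device subjects it nets 0.03 + 0.97 × 0.243 = +0.266, while the average control subject without a fatal bleed nets −0.313 (Scenario 2) or −0.462 (Scenario 1). The rule can therefore also work against the device.

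**Effect on power, Scenario 2, 65 per arm.** The death counts are assumptions. Repeated runs agree to within one or two points.

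| Early deaths, device / control | Tie rule | Death as loss |
|---|---|---|
| 1 / 0 | about 91% | about 88% |
| 3 / 0 | about 93% | about 78% |
| 0 / 3 | about 87% | about 95% |

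Without such deaths the win ratio is about 2.01. With one on device it is 2.03 under the tie rule and 1.94 if death is ranked worst; with three, 2.08 and 1.74.

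**Type I error.** With equal (control) rates in both arms and one to five such deaths on device, the tie rule rejects in 4.1% to 5.8% of trials.

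**CTD missing at random.** At 5% or 7% missing, Scenario 2 power is 90.2% or 89.3%.

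**The case against.** Limiting tier 1 to fatal bleeding within 48 h is deliberate. Protocol section 3 argues that these are the deaths the device could plausibly change. Counting any-cause death as a loss therefore asks a different question and does not repair a missing-data method. This stands, and the re-scoring proposed below should be labelled accordingly.

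The case is also narrow. The death must be non-bleeding, occur before 24 h and leave UDPB below 2, which by Protocol Table 1 means at most one unit of red cells, no plasma or platelets, and no re-exploration. One such death barely moves the win ratio. For CTD missing at random, the tie rule costs the trial a little power. All of this stands too.

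A reader might infer three stronger things that the documents do not support:
- That an early death generally outscores a device survivor. Against controls the order reverses in Scenario 1, the protocol's only scenario. In both scenarios a survivor with UDPB<2 scores higher, so part of the apparent advantage comes from conditioning the death on UDPB<2.
- That the plan hides early deaths. Protocol 9.2.1 sends every death within 30 days for adjudication, and SAP 6.3 and 6.4 tabulate mortality and fatal adverse events by arm. An imbalance would be visible; its effect on the win ratio would not.
- That the SAP has no imputation check anywhere. SAP 5.3.2 and 5.5 plan carry-forward checks for the ticagrelor and metabolite levels, but not for the primary endpoint.

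**Conclusion.** The point holds in a limited form. A non-bleeding death before 24 h with UDPB<2 and missing CTD collects wins and no losses. In Scenario 2, on which the current sample size rests, it nets slightly more against controls than the average device subject without a fatal bleed (+0.42 versus +0.37). The sensitivity analyses that Protocol 11.5 commits to are not specified for the primary endpoint, and that gap exists whether or not any such death occurs.

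The size depends on an event count the documents do not give: about 3 points of power for one device-arm death and about 15 for three, with the opposite sign when the deaths are on control. These differences measure how much the conclusion depends on the scoring of death. They are not an error in the planned test, and no false-positive inflation is shown.

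The result assumes that CTD cut short by death is treated as missing. If the partial volume were used instead, it would tend to be low and to win pairs, which also favours the subject who died.

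**What to change.** Keep the primary analysis and its alpha unchanged. Before unblinding, add to SAP 5.2.3:

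- (a) A supplementary re-scoring in which death from any cause that prevents completion of 24-hour CTD counts as a loss, labelled as a changed handling of death and not as a missing-data model.
- (b) Multiple imputation, by arm and surgery type, of CTD missing for reasons other than death.
- (c) A worst-case and tipping-point analysis in which device subjects with missing data lose and control subjects with missing data win.

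Keep the bootstrap, described only as a check on the variance. The prognostic-factor comparison promised in Protocol 11.5 can be listed in the same place.

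The cost is SAP wording and a few more runs of the existing win-ratio program. The downside for the sponsor is that a supporting result may be less favourable than the primary one.

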## **5.2.3 Sensitivity Analysis**

In order to assess the robustness of the primary effectiveness analysis a bootstrap method will be used to estimate the win ratio for the treatment. Instead of using the asymptotic variance for  $\log \widehat{WR}$ , a bootstrap resampling from the original primary effectiveness endpoint will be performed for 1000 times to obtain a bootstrap estimate of variance. With this bootstrap variance estimate, the 95% CI will be derived similarly as the primary effectiveness analysis.

## **5.2.4 Supplementary Analyses**

### **5.2.4.1 ITT analysis**

The primary effectiveness endpoint analysis will also be performed on the ITT population.

### **5.2.4.2 Per-protocol Analysis**

The primary effectiveness endpoint analysis will also be performed on the per-protocol population.

### **5.2.4.3 i-CABG Analysis**

The primary effectiveness endpoint analysis will also be performed on the i-CABG mITT and i-CABG PP populations.

### **5.2.5 Supplementary Composite Effectiveness Endpoint Analysis**

The supplementary composite effectiveness analysis will be performed on the mITT, PP, i-CABG mITT, and i-CABG PP populations in the same fashion as for primary effectiveness analyses.

### **5.3 Analysis of Key Secondary Endpoints**

All analyses will be performed on the mITT, PP, i-CABG mITT, and i-CABG PP populations.

#### **5.3.1 Key Secondary Effectiveness Endpoints**

There is no imputation for the missing pre- or post-CPB blood ticagrelor levels, and analysis will be limited to subjects who have both samples.

Percent difference in pre-CPB vs. post-CPB blood ticagrelor levels as measured by LC/MS-MS is the key secondary effectiveness endpoint.

This endpoint will be evaluated using the two-sample t-test for the percentage change in blood ticagrelor levels between the treatment and the control group. The p-value and 95% CI for this treatment difference will be provided. The model assumption will be checked using the observed data.

If the post-CPB blood ticagrelor level is below the limit of quantification (BLQ), the BLQ value will be assigned.

#### **5.3.2 Sensitivity Analysis**

Wilcoxon rank sum test based on the observed data will be performed as a sensitivity analysis. The nonparametric p-value will be provided as well as median treatment difference in percent change between pre-CPB and post-CPB blood ticagrelor levels.

The Last Measurable Observation Carried Forward method will be implemented to test the validity of imputation.

### **5.4 Analysis of Additional Secondary Effectiveness Endpoints**

All analyses will be performed on the mITT, PP, i-CABG mITT, and i-CABG PP populations.

#### **5.4.1 Continuous Secondary Effectiveness Endpoints**

The ANCOVA model with treatment group and type of surgery (when deemed appropriate) as covariates will be employed to assess the treatment difference in continuous secondary endpoints, unless specified otherwise.

##### **5.4.1.1 24-hour Chest Tube Drainage Volume**

24-hour CTD volume will be evaluated as the cumulative volume in CTD within 24 hours based on the observed data from the end of the index surgery. The subject with missing CTD volume within 24 hours due to death will be excluded from the analysis.

The ANCOVA model with treatment group and type of surgery (when deemed appropriate) as covariates will be employed to assess the treatment difference in 24-hour CTD. The p-

value and estimated mean difference along with the 95% CI will be provided between the treatment and control group.

#### **5.4.1.2 Other Continuous Secondary Effectiveness Endpoints**

Total platelet/PRBC transfusions in volumes from end of operation through the duration of the index hospitalization (initial discharge from the hospital) will be analyzed based on the observed data using two-sample t test. The p-value and estimated mean difference along with the 95% CI will be provided between the treatment and control group.

Wilcoxon rank sum test based on the observed data in volumes will be performed if the normality assumption is invalid. The nonparametric p-value will be provided as well as median treatment difference in volumes for total platelet/PRBC transfusions.

The same analyses using transfusion data measured in units will be conducted as the supplemental analyses.

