The UDPB scale is a standardized bleeding definition that was specifically designed by experts to capture early bleeding after cardiac surgery and is based on the following 9 criteria occurring either in surgery or during the first postoperative day: (1) delayed sternal closure, (2) postoperative chest tube output, (3) packed red blood cell transfusion, (4) fresh frozen plasma transfusion, (5) platelet transfusion, (6) cryoprecipitate transfusion, (7) use of factor concentrates, (8) use of recombinant activated factor VII (rFVIIa), and (9) surgical re-exploration. [17] The UDPB scale defines 5 perioperative bleeding classes (0-4) as shown in **Table 1** (below). Importantly, it has been demonstrated that higher classification within the UDPB (starting from moderate, up through severe-massive) is correlated with higher 30-day mortality rate, thus making the standardized definition both a useful descriptive tool as well as a predictor of clinical outcome. [17]

Table 1. Bleeding Class According to the Universal Definition of Perioperative Bleeding in Adult Cardiac Surgery

Class	Sternal Closure delayed	Postoperative chest tube blood loss within 12 h (mL)	PRBC (units)	FFP (units)	PLT (units)	Cryoppt	PCCs	rFVIIa	Reexploration/tamponade
0	No	< 600	0*	0	0	No	No	No	No
1	No	601-800	1	0	0	No	No	No	No
2	No	801-1000	2-4	2-4	Yes	Yes	Yes	No	No
3	Yes	1001-2000	5-10	5-10	N/A	N/A	N/A	No	Yes
4	N/A	>2000	>10	>10	N/A	N/A	N/A	Yes	N/A

Class 0 = Insignificant; Class 1 = Mild; Class 2 = Moderate; Class 3 = Severe; Class 4 = Massive

PRBC = packed red blood cells; FFP = fresh frozen plasma; PLT = platelet concentrates; Cryoppt = Cryoprecipitate; PCCs = prothrombin complex concentrates = rFVIIa, recombinant activated factor VII; N/A, not applicable

For purposes of UDPB, PRBC, PLT, FFP, and Cryoppt transfusions are counted beginning **at chest closure**. PCC and rFVIIa transfusions are counted beginning at the start of the procedure.

* Correction of preoperative anemia or hemodilution only; the number of PRBCs used should only be considered in the UDPB when accompanied by other signs of Perioperative bleeding. Prophylactic/preoperative transfusion of blood products and factor concentrates do not contribute to UDPB.

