Benchtop studies of drug removal by the DrugSorb™-ATR device (CytoSorbents, unpublished data) demonstrate concentration and time dependent absolute drug removal. Based on these benchtop studies, a conservative estimate of 40% reduction in blood concentration of ticagrelor between pre- and post- DrugSorb™-ATR removal is expected, with a standard deviation of 40%, in the treatment arm. Minimal change is expected in the control arm. A two-sample t-test will be used to evaluate the difference between treatment arms. Due to highly variable baseline ticagrelor blood levels in the above benchtop studies, percent change from baseline will be analyzed as opposed to observed values. We anticipate drug removal data from other clinical studies in this application to become available during the course of the study and we plan to update the above assumption if necessary based on *in vivo* data.

Additional powered secondary endpoints include 24-hour CTD (volume [mL]), total platelet transfusions during the index hospitalization (volume [mL] and units), and total PRBC transfusions during the index hospitalization (volume [mL] and units). Twenty-four-hour CTD (mL) will be assessed via two-sample t-test for mean difference. In the event the assumptions for a two-sample t-test are not met, a nonparametric test such as a Mann-Whitney test will be employed, with median and range values provided in the output. The transfusion endpoints will all be analyzed using two-sample t-tests for mean differences, and Fisher-Freeman-Halton exact tests for units. In the event the assumptions for a two-sample t-test are not met, a nonparametric test such as a Mann-Whitney test will be employed, with median and range values provided in the output. Other secondary endpoints include the remaining Win Ratio component parts: proportions of fatal perioperative bleeding events will be assessed via Fisher’s exact test; and proportions of UDPB events (by category) will be

assessed via a Fisher-Freeman-Halton exact test. All surgical re-exploration for excessive bleeding, including those events occurring beyond the timeframe captured within the UDPB component of the primary endpoint will be captured as a secondary endpoint. Time to re-exploration will be taken into account.

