## 2 SAMPLE SIZE AND STATISTICAL POWER CONSIDERATION

The hypothesis for the primary effectiveness endpoint will be tested using Finkelstein-Schoenfeld test (Finkelstein et al 1999). With the assumed effect sizes and variability for Scenario 1 outlined in Table 1 (Section 11.1 of the CIP), 57 subjects per arm will provide >99% power for the primary effectiveness endpoint based on Finkelstein-Schoenfeld test statistics at the two-sided significant level alpha ( $\alpha$ ) of 0.05. Taking into consideration higher than anticipated variability observed with the 24hr CTD variable, in scenario 2 we consider the same effect sizes in the 3 components and a larger variability (double of that in Scenario 1). In that instance the needed sample size is 65 per arm to achieve 92% power.

With this same sample size per arm, power for the key secondary endpoint is estimated >99.9%, and for 24-hour chest tube drainage (mL), >99.9%, based on a two-sample t-test assuming equal variance and a two-sided alpha of 0.05. Assuming unequal variances, power for comparisons of platelet transfusions (volume [mL]) and PRBC transfusions (volume [mL]), is estimated at 98.0% and 96.7%, respectively.

Allowing for ~7% dropouts, approximately 140 subjects will be randomized in a 1:1 ratio to the treatment and control arms to ensure that 130 subjects (65 per arm) will be evaluable for the primary effectiveness analysis.

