**Table 1. Effect Size Assumptions with Power and Sample Size Estimates**

Scenario	Sample size Per Group	Effect Size						Power	
		Component #1		Component #2		Component #3			
		Fatal Bleeding		UDPB (Class ≥2)		24hr CTD			
Treatment Event	Control Event	Treatment Event	Control Event	Treatment Mean (SD)	Control Mean (SD)				
1	N= 57	3.0%	3.0%	24.3%	40.5%	480 (253)	800 (253)	99.7%	
2	N=65	3.0%	3.0%	24.3%	40.5%	480 (500)	800 (500)	92.1%	

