### **5 STATISTICAL ANALYSIS METHODS**

#### **5.1 General Considerations**

Unless otherwise specified, all statistical analyses will be performed on the mITT population.

In general, summary statistics (n, mean, SD, median, minimum, and maximum for continuous variables, and number and percentage of subjects in each category for categorical variables) will be provided by treatment. All summary tables will be based on the observed data unless specified otherwise. Source data for the summary tables and statistical analyses will be presented as subject level data listings.

The two-sided significance level of 5% is used for the hypothesis testing, unless specified otherwise.

Fixed sequence testing procedure will be utilized to compare the effectiveness of the treatment vs control in the following order:

Primary endpoint → Key secondary endpoint → Additional Secondary endpoints (24hr CTD → platelet transfusions → PRBC transfusions → UBPB events by class → surgical re-exploration for excessive bleeding → fatal perioperative bleeding event)

The significance for the secondary endpoints will only be considered if the primary endpoint is declared statistically significant and the p-value of the previous endpoint is less than 5%, otherwise, the testing procedure stops, and all the subsequent p-values will be nominal.

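### If platelet volume goes to the Wilcoxon fallback, the SAP pairs the p-value with an undefined median difference that is likely to be exactly 0 mL under the plan's UDPB rates

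*SAP*

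**What the plan says.** SAP 5.4.1.2 compares total platelet and PRBC volume, from the end of the operation to initial hospital discharge, by two-sample t-test. Its first paragraph promises a p-value, a mean difference and a 95% CI. If the normality assumption is invalid, a Wilcoxon rank sum test is used: "The nonparametric p-value will be provided as well as median treatment difference in volumes for total platelet/PRBC transfusions". The section does not say how normality is judged, whether the median difference is a difference of arm medians or a Hodges-Lehmann estimate, or what interval goes with it. Transfusions in units are analysed in the same way as a supplement.

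Protocol 11.3 has a similar fallback: "a nonparametric test such as a Mann-Whitney test will be employed, with median and range values provided in the output". SAP 5.1 gives mean, SD, median, minimum and maximum by arm for every continuous variable.

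Platelet transfusion is the fourth test in the fixed sequence of SAP 3.7 and 5.1, after the primary endpoint, drug removal and 24-hour chest tube drainage. PRBC is the fifth. SAP 5.4 repeats these analyses in four populations.

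**The concern.** Many subjects will receive no platelets after the operation. Under protocol Table 1 (section 3), UDPB classes 0 and 1 have zero platelets, so any counted platelet transfusion puts a subject in class 2 or higher. Counting for UDPB starts at chest closure ("For purposes of UDPB, PRBC, PLT, FFP, and Cryoppt transfusions are counted beginning" at that point), which is close to where the SAP's transfusion endpoint starts. SAP Table 1, "Effect Size Assumptions with Power and Sample Size Estimates", assumes class 2 or higher in 24.3% of device and 40.5% of control subjects. If those rates limit platelet use, more than half of each arm is expected to have zero volume, and both medians are then zero.

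The trial could then report a significant Wilcoxon result for an alpha-controlled endpoint beside an effect estimate of 0 mL, even though mean platelet use had fallen clearly.

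**Working it through.** **Inputs.** Two-sided alpha 0.05 (SAP 5.1). 65 evaluable per arm (SAP section 2), with 57 (protocol 11.1) and 70 (all randomized) also run. Platelets 0.32 (SD 0.9) vs 1.6 (SD 2.2) units and PRBC 1.3 (2.1) vs 4.4 (5.7) units (protocol 11.1). UDPB class 2 or higher 24.3% vs 40.5% (protocol Table 3, SAP Table 1). The documents give no volume per unit, but zero units is zero mL, so the zero-median results do not need one.

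**The plan's own power, reproduced.** Unequal-variance t-test, noncentral t, n = 57 per arm:
- Platelets: SE = sqrt((0.9² + 2.2²)/57) = 0.315; noncentrality 1.28/0.315 = 4.07; power 97.99% (stated 98.0%).
- PRBC: SE = sqrt((2.1² + 5.7²)/57) = 0.805; noncentrality 3.1/0.805 = 3.85; power 96.71% (stated 96.7%).

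**Is the fallback likely?** Both platelet SDs exceed their means (0.9 > 0.32; 2.2 > 1.6) on a non-negative variable, so the data cannot be close to normal.

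**Chance of a zero difference of medians at the UDPB rates.** Suppose every class 2 or higher subject, and nobody else, receives platelets. An arm's median is 0 when at most 28 of 57, 32 of 65 or 34 of 70 subjects are transfused. By the exact binomial:

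| n per arm | Control (40.5%) | Device (24.3%) | Both medians 0 |
|---|---|---|---|
| 57 | 92.7% | >99.99% | 92.7% |
| 65 | 94.0% | >99.99% | 94.0% |
| 70 | 93.2% | >99.99% | 93.2% |

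Class 2 can also be reached by other criteria. If only 75% of class 2 or higher subjects receive platelets, the figure at n = 65 exceeds 99.9%.

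**Given a significant Wilcoxon test (simulation).** The share transfused was set at the UDPB rates. Amounts among those transfused were matched to the protocol's moments: control mean 1.6/0.405 = 3.95 units (SD 1.63), device mean 0.32/0.243 = 1.32 units (SD 1.42). The difference of medians is still 0 in about 91-93% of significant trials for n = 57 to 70. With equal amounts in both arms among those transfused (n = 65), it is 87%. Hodges-Lehmann does not cure this: it is 0 in about 94-99% of significant trials.

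**Sensitivity to platelets outside UDPB.** The control share reaches one half after 50 - 40.5 = 9.5 further points. Assuming the same extra share in each arm, at n = 65:

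| Extra points per arm | Zero difference of medians |
|---|---|
| 0 | 94% |
| 5 | 77% |
| 10 | 46% |
| 15 | 18% |

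**Using the protocol's platelet moments instead.** For a non-negative variable the non-zero share is at least mean²/(mean² + SD²). For controls that is 2.56/(2.56 + 4.84) = 34.6%, so these inputs alone do not fix the median. As a negative binomial (an assumption), k = 2.56/(4.84 - 1.6) = 0.790 and P(0) = (0.790/2.390)^0.790 = 41.7%. Then 58.3% of controls are transfused, their median is 1 unit, and the difference of medians is 0 in about 9% of trials at n = 65.

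**PRBC.** A negative binomial with the protocol's moments gives a zero difference of medians in about 2% of trials.

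**What other measures show under the UDPB-rate model.** Mean difference 0.32 - 1.6 = -1.28 units; share transfused 24.3 - 40.5 = -16.2 points.

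**The case against.** A reader might infer that the trial could not say how much blood product is saved. The documents do not support that. The first paragraph of SAP 5.4.1.2 promises the mean difference and 95% CI with no condition attached, and SAP 5.1 gives arm means in any case. What stands is narrower. That sentence follows the t-test, the next paragraph names different output for the fallback, and the SAP does not say whether both are kept or which leads. If the mean difference is kept, its CI is the t-based one whose assumption has just been rejected.

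A reader might also infer that the platelet median difference is almost always zero. The UDPB rate is not a ceiling for this endpoint. UDPB covers surgery and the first postoperative day and leaves out prophylactic transfusion, while the endpoint runs to discharge. About 10 further points of platelet use per arm brings the figure below one half, and the protocol's own platelet moments are compatible with a control median of 1 unit. This objection stands. In return, the negative binomial reading needs 58.3 - 40.5 = 17.8 points of controls to receive platelets only outside UDPB, and the documents do not settle which picture applies.

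Extending the point to PRBC is tempting, because classes 0 and 1 allow at most one unit. It fails. The footnote to protocol Table 1 leaves out red cells given for anemia or hemodilution without other signs of bleeding, later units fall outside UDPB, and the protocol assumes means of 1.3 and 4.4 units.

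Finally, since the SAP gives no criterion for judging normality, the t-test might be kept at 65 per arm on large-sample grounds. The issue would then not arise, but the SAP's stated trigger is normality itself.

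**Conclusion.** The point holds for platelets as a defect in the reported effect measure. It does not affect the p-value, the type I error or the testing order. At the plan's UDPB rates the difference of medians is exactly 0 mL in about 93-94% of trials, and in about 87-93% of those with a significant Wilcoxon test. This assumes that the share given platelets is no higher than those rates. The range under other assumptions is wide, from above 99.9% down to about 9%, and the documents give no rate of platelet use outside the UDPB window. An effect measure whose usefulness depends on that unknown is a poor choice for an alpha-controlled endpoint, all the more without a defined estimator or an interval. The correction should be made before unblinding, so that the effect measure is not chosen after the data are seen.

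**What to change.** In SAP 5.4.1.2, state: *When the Wilcoxon test is used, the reported effect is the difference in mean volume with a bootstrap 95% CI, together with the percentage of subjects transfused in each arm and the risk difference with 95% CI. The median difference may be given as a descriptive statistic, with its estimator named.* Apply the same to the analysis in units.

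The cost is one SAP addition and a few lines of code and output, with no new data. One small downside is that the mean difference is not the quantity the rank test tests, so the two can point to different sizes of effect. The SAP should say so beside the result.
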